### Abstract

The long head of the biceps can be a source of anterior shoulder pain that is primarily due to inflammation or instability of the long head of the biceps (LHB) tendon.

Patients that fail non-operative management become candidates for biceps tenotomy and tenodesis. Currently, there is no universal protocol or gold standard for how the LHB tendon is tensioned. At our institution, the LHB is tensioned based on individual surgeon feel for the correct tensioning. The purpose of this study is to conduct a randomized, single-blinded prospective study comparing patients of the current regimen of bicep tensioning vs. utilizing a standardized method of anatomically tensioning the LHB tendon. The primary aim of assessing change in the American Shoulder and Elbow Surgeon (ASES) scores from baseline to post-surgery between the control and intervention groups will be assessed using a student's t-test. In addition, longitudinal mixed effects models will be used to estimate changes in ASES scores, over all time-points using a random effect for surgeon. Other relevant patient characteristics such as age, sex, and Charlson score will be included to explore the adjusted relationship of the intervention and outcomes over time. A secondary aim of this study is to collect specific measurements of the myotendinous junction of the LHB tendon to potentially establish if any characteristics predispose patients to developing pathology of the LHB tendon.

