### **IV. Study Design**

- a. Experimental Design: Patients that meet the inclusion/exclusion criteria will be eligible for participation in the study. The design will be a single blinded format where the surgeon will be aware of what treatment the patient will receive (Control vs. Intervention). The patient will not be informed of what arm of treatment they were selected for. Block randomization will be utilized to place an equal number of patients into both groups.
- b. Study Population: Patients undergoing arthroscopic shoulder surgery with long head of the biceps tendon pathology.
- c. Sample size determination and power analyses:  
Based on previous studies, it is assumed that the pre-ASES score for all patients undergoing biceps tenodesis is approximately 45. At 1 year post surgery, the standard of care group will increase to 85 (Mean difference = 40, STD=18). It is hypothesized that the treatment group with anatomical fixation will increase to approximately 93 (Mean difference = 48, STD=18).

The necessary sample size was calculated using 80% power of rejecting the null hypothesis (that there is no difference in change in ASES scores between the two groups of interest), when the population mean difference in ASES is  $\Delta 1 - \Delta 2 = 48 - 40 = 8$ , with a standard deviation of 18, and with a significance level (alpha) of 0.05. This power and sample size calculation was computed using a two-sided two-sample equal-variance t-test.

To achieve this power, at least 81 patients will need to be enrolled in each group. Patients will only be randomized once to this study. If a patient has a repeat surgery, that case will not be eligible for randomization.

- d. Study outcomes/endpoints
  - i. Study endpoint will be decided based on the power analysis that was calculated by the research team biostatistician.
  - ii. Data collected:
    1. Demographics: Name, MRN, age, sex, hand dominance, ethnicity, profession, BMI

2. Clinical Factors: Indication for surgery, procedures performed, past medical history of upper extremity pathology
3. Medical History: Myocardial infarction, congestive heart failure, peripheral vascular disease, transient ischemic attack or cerebrovascular accident, dementia, chronic obstructive pulmonary disease, connective tissue disease, peptic ulcer disease, liver disease, diabetes, hemiplegia, chronic kidney disease, solid tumor, leukemia, lymphoma
4. Measurements: (in mm)

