- a. At the patient's initial clinical visit, they will be given a copy of the informed consent that details specifics of the research study that we are conducting. It will be translated into a health comprehension level deemed appropriate by the IRB committee (7th grade).

- iii. Screening procedures

1. What procedures are required for screening?

- a. At the initial outpatient office visit, qualifying patients will be further screened using the aforementioned inclusion/exclusion criteria. At that time, [name] or [name] will speak with the patient about the research study to its entirety, which will include the potential benefits, risks and alternatives.

2. What is the screening schedule (number of visits, length of visits)?

- a. Patient will be screened during their initial outpatient office visit.
- b. Those patients that express interest will again be approached on the day of surgery. On this day, a member of the research team will explain to the patient, for the second time, the research project.

3. Which screening tests/procedures are part of standard care and which are for research purposes only?

- a. A member of the research team will be at the office visit to obtain an ASES score prior to surgery and will contact patients via phone at 2 weeks, 6 weeks, 3 months, and 6 months and one year after surgery.
  - b. Standard of Care: Aspects of the physical examination including range of motion, strength, neurovascular status, and shoulder/elbow specific testing will be recorded by the surgeon in the chart per standard history and physical documentation.
    - i. A member of the research team will gather this information via chart review.
  - c. Research Specific: On the day of surgery, a member of the research team will ask the patient a short series of questions in order to calculate an American Shoulder & Elbow Surgeon (ASES) score as their preoperative score. The member of the research team administering the questionnaire will not be blinded. A specific description of the ASES questionnaire is detailed later in the protocol. This questionnaire will again be tested at the patient's 6 month follow up.
4. What happens with screen failures (including any data gathered during screening)?
  - a. Those patients that are not eligible based on the inclusion/exclusion criteria, will not be included in the study.

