  - b. The risk of patients incorrectly being included in the study despite screening the inclusion/exclusion criteria is essentially zero.
    - i. All female patients are screened day of surgery with a pregnancy test.
    - ii. Age of patient is obtained & confirmed at all clinical encounters.
    - iii. History of prior surgery is obtained and verified at initial clinical visit.
- b. Randomization procedures
  - i. Surgeon block randomization scheme will be used. This will be 1-1 stratified for [name] and [name].
  - ii. Each surgeon will receive a stratified block randomization list provided by the department of Biostatistics and will be used for patients in chronological order for the surgical start time. Both surgeon schedules are accommodating of this because they are in the operating room on different days of the week.
  - iii. Prior to the start of the surgery, the surgeon will be notified by a member of the research team if the patient will be part of the control group or the anatomic fixation group.

- c. Study Intervention
  - i. Control Group: The control group patient will undergo biceps tenotomy and tenodesis based on surgeon feel on appropriate tensioning of the tendon (Current practice).
    - 1. Of note, there is no universal method or gold standard on how the long head of the biceps should be tensioned during bicep tenodesis.
  - ii. Intervention Group: Patients that are randomized to the intervention group will undergo biceps tenodesis in a standardized, step-by-step protocol as outlined below
- d. Surgical Procedure Overview
  - i. The initial indication for tenodesis is at the surgeon's discretion, but after that decision is made, then the Control vs. intervention is determined based on our randomization scheme.
  - ii. Per current surgeon protocol, all patients will receive a single injected pre-operative nerve block and standard post-operative pain regimen.
  - iii. As with every shoulder arthroscopy, a diagnostic scope of the shoulder will be performed, which will include evaluation of the intra-articular portion of the long head of the biceps tendon. If there is any instability or tendinopathy, then the surgeon will decide if biceps tenotomy and tenodesis is indicated.
  - iv. Surgical Steps: Biceps Tenotomy & Tenodesis

\*Bolded steps are deviation from current, standard surgeon protocol

1. Positioning of the patient will be in the standard beach chair position

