14. The tendon is shortened
15. The sutures from the biceps are passed through the Arthrex cortical button
16. The pectoralis major tendon is retracted and 2 centimeters proximal to the distal insertion a unicortical bone tunnel is drilled in the bicipital groove with a 3.2 millimeter drill
17. The wound is irrigated and the biceps button is threaded into this tunnel and then flipped. The suture is tensioned, securing the biceps against the groove
18. The skin is closed in the usual fashion

e. Study Assessments and Activities

- i. If indicated, patients will undergo biceps tenodesis, as described above
  1. Standard protocol for [name] and [name] is for patients to follow up at 2 weeks, 6 weeks, 3 months, and 6 months after surgery.
    - a. A member of the research team will be at the office visit to obtain an ASES score prior to surgery and will contact patients via phone at 2 weeks, 6 weeks, 3 months, and 6 months and one year after surgery.

- b. A member of the research team will retrospectively collect history and physical examination data using [name] or [name] notes (Complications, Range of motion, strength, special shoulder or elbow physical exam tests).
2. Once the patient has completed their 6 month follow up appointment, all identifiable data from that patient will be deleted from all research records.

[figure not shown]

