### **VIII. Statistical Analysis Plan**

The primary aim of assessing change in the ASES score from baseline to post-surgery between the control and intervention groups will be assessed using a student's t-test, as indicated in the study design.

In addition, longitudinal mixed effects models will be used to estimate changes in ASES scores, over all time-points using a random effect for surgeon. Other relevant patient characteristics such as age, sex, and Charlson score will be included to explore the adjusted relationship of the intervention and outcomes over time.

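### The primary t-test on change in ASES is valid but leaves precision unused: make baseline-adjusted ANCOVA primary, and state that 81 per group is the number analysed, not enrolled

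*Combined protocol and SAP*

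**What the plan says.** Section VIII states that the primary aim, change in ASES between the groups, "will be assessed using a student's t-test, as indicated in the study design". The abstract says the same: "scores from baseline to post-surgery between the control and intervention groups will be assessed using a student's t-test". Neither sentence names a time point, but the reference to the study design leads to section IV.c, which sizes the trial on change at 1 year: "At 1 year post surgery, the standard of care group will increase to 85" from about 45 in the control group, and to about 93 in the intervention group. The mean changes are 40 and 48, each with SD 18. The calculation uses a two-sided equal-variance t-test, alpha 0.05 and 80% power, and concludes: "To achieve this power, at least 81 patients will need to be enrolled in each group".

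On randomization, section V.b says "Surgeon block randomization scheme will be used", stratified 1:1 for two surgeons. A mixed model over all time points is planned in addition, with a random surgeon effect and age, sex and Charlson score. Baseline ASES is not named as a covariate in either analysis.

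The baseline questionnaire is given on the day of surgery "in order to calculate an American Shoulder & Elbow Surgeon (ASES) score as their preoperative score" (section V.a.iii); the same section and section V.e also mention a score taken at an office visit. On follow-up, V.a.iii says "This questionnaire will again be tested at the patient's 6 month follow up". Section V.e says standard clinic practice "is for patients to follow up at 2 weeks, 6 weeks, 3 months, and 6 months after surgery", with ASES obtained by phone at those times and at one year.

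**The concern.** A t-test on change uses baseline only by subtraction, which amounts to a regression with the baseline coefficient fixed at 1. ANCOVA estimates that coefficient. Under randomization both are valid, but the ANCOVA residual variance is never larger in large samples, and it is smaller unless the true slope is 1. The baseline score is collected anyway. The stratification factor is also left out of the primary test, although that matters less.

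The second issue is the label on 81. If it is an enrolment figure with no allowance for loss, the stated 80% power holds only when every enrolled patient has a 1-year score, and a reader of IV.c cannot see this. Some loss is plausible: routine clinic visits stop at 6 months, the 1-year score depends on a phone call, and section VI allows withdrawal at any time.

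**Working it through.** **Inputs from section IV.c:** difference in mean change 8; SD 18, printed beside the mean change and so read as the SD of change; two-sided alpha 0.05; 1:1 allocation; 81 per group.

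**Assumed, because the documents do not give them:** the correlation ρ between baseline and 1-year ASES; the ratio k of the 1-year SD to the baseline SD; the loss rate; the share of variance due to surgeon.

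**1. The plan's own figure.** The two-sample t-test (noncentral t) with effect size 8/18 needs n = 80.44 per group, rounded up to 81. Power at 81 is 80.3%. The stated number reproduces and contains no allowance for loss.

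**2. Residual SDs.** Write s0 and s1 for the baseline and 1-year SDs, with k = s1/s0.

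- Variance of change: s0² + s1² − 2ρ·s0·s1.
- ANCOVA residual variance: s1²(1 − ρ²).
- Difference: (s0 − ρ·s1)², which is never negative and is zero only when the slope ρk equals 1.

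Holding the SD of change at 18:

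- ANCOVA residual SD = 18·k·√[(1 − ρ²)/(1 + k² − 2ρk)]
- implied 1-year SD = 18·k/√(1 + k² − 2ρk)

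**3. Power at 81 analysed per group, and 95% CI half-width.** The half-width is t × residual SD × √(2/81). For the t-test this is 1.975 × 18 × 0.1571 = 5.59 points.

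| Analysis | k | ρ | Slope ρk | Residual SD | 1-year SD | Power | Half-width |
|---|---|---|---|---|---|---|---|
| t-test on change | – | – | fixed at 1 | 18.00 | – | 80.3% | 5.59 |
| ANCOVA | 1 | 0.3 | 0.30 | 14.51 | 15.2 | 93.7% | 4.50 |
| ANCOVA | 1 | 0.5 | 0.50 | 15.59 | 18.0 | 90.1% | 4.84 |
| ANCOVA | 1 | 0.7 | 0.70 | 16.60 | 23.2 | 86.2% | 5.15 |
| ANCOVA | 1.25 | 0.5 | 0.625 | 17.01 | 19.6 | 84.5% | 5.28 |
| ANCOVA | 1.5 | 0.5 | 0.75 | 17.68 | 20.4 | 81.7% | 5.49 |
| ANCOVA | 1.4 | 0.7 | 0.98 | 18.00 | 25.2 | 80.3% | 5.58 |
| ANCOVA | 0.8 | 0.5 | 0.40 | 13.61 | 15.7 | 96.1% | 4.22 |

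**4. Bound from the scale.** With a mean of 93 on a 0–100 scale, the SD cannot exceed √(93 × 7) = 25.5. With equal SDs this gives ρ ≤ 1 − 324/(2 × 651) = 0.751, where the residual SD is 16.84 and power is 85.2%.

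**5. Simulation.** In 20,000 runs with 81 per arm, ANCOVA on group, baseline and surgeon (k = 1, ρ = 0.3/0.5/0.7) had power 93.5/89.7/85.9%, against 80.1/79.9/80.0% for the t-test. Type I error was 5.1/4.9/4.9% and 5.0/5.0/5.0%.

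**6. Surgeon.** If surgeon explains 1–5% of the variance, t-test power of 80.3% becomes 80.7–82.2% after adjustment: a small gain.

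**7. Loss from 81 enrolled per group.**

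| Loss | Expected analysed | Rounded to nearest: n, t-test power | Rounded down: n, t-test power |
|---|---|---|---|
| 10% | 72.9 | 73, 76.0% | 72, 75.4% |
| 15% | 68.85 | 69, 73.6% | 68, 73.0% |
| 20% | 64.8 | 65, 71.0% | 64, 70.4% |

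At 65 analysed, ANCOVA with k = 1 and ρ = 0.5 still has 82.7% power. Keeping 81 analysed would instead mean enrolling 81/(1 − loss) = 90, 96 or 102 per group.

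**The case against.** The plan is internally consistent: the abstract, IV.c and VIII all name one valid test, and surgeon and patient covariates already appear in the mixed model. Choosing ANCOVA could be called a preference. That is a fair description of its weight, but not a reason to decline a gain that costs nothing.

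The size of the gain cannot be taken from the documents. Combinations within the scale bound give almost none: k = 1.4 with ρ = 0.7 returns 80.3%, and k = 1.25 with ρ = 0.7 returns 81.0%. Both need a 1-year SD of about 25, close to the limit that requires every patient to score 0 or 100. The case k = 1.5 with ρ = 0.5 is less extreme and gives 81.7%. So the range stands as a range, and no single figure should be promised. In none of these cases does ANCOVA do worse than the t-test.

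Scores near the ceiling also make normal-theory power approximate. With mean 93 and SD 15.2 to 23.2, a normal curve puts about 32 to 38% of the intervention arm above 100. This limits the precision of every power figure here, including the plan's own. Bunching that shrinks the 1-year SD would enlarge the gain.

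Some drafting points stand. IV.c says at least 81, which permits more. If ANCOVA becomes primary, IV.c should say that 81 was kept as a conservative t-test size. The mixed model should not be relied on to supply the baseline adjustment, because its listed covariates omit baseline ASES.

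**Conclusion.** The concern holds. The sample size arithmetic is correct and the t-test keeps its error rate, so this is an efficiency improvement plus a labelling correction. The change should be made, but the trial is not invalid without it. With equal SDs and correlations of 0.3 to 0.7, power at 81 analysed rises from 80.3% to between 86 and 94%, and the confidence interval narrows by 0.4 to 1.1 points on each side. The gain is smaller if 1-year scores are more variable than baseline scores, and nil at a slope of 1.

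The enrolled/analysed point needs no assumption about correlation: 81 has no allowance for loss, and none appears elsewhere in the text available for review, from which some passages had been removed. How far power falls depends on the loss rate, which is assumed. All of this reads 18 as the SD of change.

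**What to change.** **Section VIII, with the matching sentence in the abstract.** Replace the primary analysis with:

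> The primary analysis is an ANCOVA of ASES at 1 year on treatment group, baseline ASES and surgeon (fixed effect), two-sided alpha 0.05, reporting the adjusted mean difference with 95% CI. The t-test on change from baseline to 1 year is a sensitivity analysis.

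Name the day-of-surgery score as the baseline, since V.a.iii designates it the preoperative score, and say how the office-visit score relates to it. Keep the mixed model as supporting analysis, since it can use partial follow-up.

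**Section IV.c.** Add:

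> Eighty percent power assumes 81 patients per group analysed at 1 year, based on a t-test on change with SD of change 18. This number is kept as conservative for the ANCOVA. With an assumed 10/15/20% loss from 81 enrolled, t-test power is about 76/74/71%.

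If the sponsor prefers to protect t-test power by enrolment, the targets are 90, 96 or 102 per group at those loss rates.

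**Reconcile the follow-up text.** IV.c and V.e refer to a 1-year score, while V.a.iii describes repeating the questionnaire at 6 months. V.e deletes a patient's identifiable data after the 6-month visit, although the 1-year phone call comes later; VII.b deletes identifiers on study completion. Read literally, V.e could prevent collection of the endpoint on which the trial was sized.

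**Cost.** Wording only, in the abstract, IV.c, V, VII and VIII. No extra patients, visits or data items, unless the sponsor chooses the larger enrolment.
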